5.3 Device Use

The device can be used for screening purposes but in this study the device will be used as a site specific technique intended to be used where a dentist has already detected a potential carious lesion. The dentist will have carried out a standard oral examination to detect and assess potential caries lesions. Where a potential lesion is detected and the dentist would like more information about that lesion, i.e. is there on-going active loss of calcium ions (de-mineralization) from that lesion, use of the Calcivis System may be appropriate. In normal operation, the dentist will image a tooth before application of the Disclosing Solution using the Calcivis intraoral camera. The Disclosing Solution will then be applied to the same tooth and another image will be taken with the Calcivis camera. The image is processed by the software then displayed on a PC monitor and can then be printed and / or stored to hard disk or incorporated on to dental practice imaging management systems. The system is fully automated so that both images are taken within less than 0.5 seconds (including the automated application of the disclosing solution).

[figure not shown]
Full details for the operation of the Calcivis System is supplied in the Instructions For Use.

5.4 Device Technology

The Calcivis System technology involves imaging localised calcium loss from demineralizing tooth surfaces, as evidenced by the luminescence, or light emission (low level in visible spectrum), produced from the ionic calcium interacting with the Disclosing Solution (containing photoprotein), after it is applied to the tooth surface. The light emission results from a chemical reaction between the photoprotein and free Calcium, in contrast to fluorescence based technologies which require an excitatory light source.

The Disclosing Solution is placed on to a tooth and where ionic calcium is present light is generated which the intraoral camera detects and records. The majority of the light signal is captured in less than 0.1 second. Software is used to overlay the visible and luminescent images in order to highlight regions where calcium ions are present, providing an easy to use interface, thereby providing de-mineralization maps of the tooth surfaces which are interpreted by the Dentist. Figure 3 below summarizes this process.

Figure 3: Summary of visualization of free calcium by Calcivis System

Typical white spot lesions can be seen on the visible images of freshly extracted teeth (1A to 3A – black and white images).

Luminescent images of the same three teeth (1B to 3B) and false-coloured luminescent images (1C to 3C). Both these types of images show the observed pattern of luminescence from the tooth surface after the addition of disclosing solution

Merged images of the black and white images with the false-coloured luminescent images (1D to 3D) which show the positioning of the luminescent pattern on the tooth surface for each of the three teeth.

5.5 Device Manufacture

The Calcivis system intra-oral imaging device will not normally come into contact with the skin, teeth or mucosa of the patient. It will be covered by a single use, disposable applicator, which may come into contact with the skin, teeth and mucosa of the patient, to protect the patient from any possible cross-contamination from the multi-use camera unit. The imaging unit will be cleaned thoroughly between use with hospital grade disinfectant wipes. The camera connects directly with the USB of a PC and incorporates a CMOS system, Light Emitting Diode (LED) – visible light and a lens to capture the image. Images can be transferred to the PC for display by the software.

The Disclosing Solution comprises a lyophilized, powdered recombinant bioluminescent protein. By supplying the disclosing solution lyophilized, it maximizes the shelf life and specificity of the bioluminescent capability. The powder will be supplied non-sterile but low bioburden and will be reconstituted immediately before use with deionized water (also supplied). A total of 2.5 µg (100µg/ml in 25µl application) of photo-protein is dispensed per application in the disclosing solution.

5.6 Regulatory Status

EU

The **Calcivis System** is classified in the EU as a Class IIa Medical Device according to the Medical Device Directive.

The Calcivis System comprises three components as follows:

Device (Intra-oral Camera) - administration and Imaging device

Class IIA Rule 11 for administration of disclosing solution,

Class I Active Rule 12 for imaging

Class I Active Rule 12 for Software

(Therefore the highest class is Class IIA Rule 11)

Disclosing Solution – lyophilised protein and water for reconstitution

Class I Rule 5 invasive (via natural orifice) and transient. Intended to bind with free calcium ions at the tooth surface and emitted light (in visible spectrum) captured by the imaging system.

Disposables – applicator, syringe and needleless

Class I Rule 5 invasive (via natural orifice). Syringe and needleless adaptor to be provided sterile until open.

USA

The Calcivis System falls under 'diagnosis, prevention, monitoring, treatment or alleviation of disease, and does not achieve its action by pharmacological, immunological or metabolic means'. The Calcivis technology involves the detection and display of a chemical reaction as part of caries lesion activity assessment, which includes imaging localised calcium loss from demineralizing surfaces. This is only one of several factors which can be used to diagnose caries. Elevated levels of calcium ions can also be a result of a number of different causes (dental erosion, dental fluorosis and enamel hypomineralisation). The dentist therefore has to consider all potential causes before making a diagnosis. Thus, the Calcivis System has the potential for showing activity of caries and is an aid to the dentist, and not diagnostic *per se*.

5.7 Device Safety

Clinical and Pre – Clinical Data

As the mode of action of the Calcivis Device is detection of free calcium on the tooth surface it is relatively simple to check this function using calcium solutions of varying concentration in wells and confirm using extracted teeth. Release testing of the disclosing solution includes a functional assay employing stopped-flow technology. The stopped flow process uses fixed syringes to rapidly (within a few nanoseconds) dispense set volumes of known concentration of the luminescent marker and 1mM calcium chloride to a mixing chamber, from which light output is collected and assessed. The intra-oral imaging device can be set up in a dark box or “mock mouth” with either wells of calcium solution or extracted teeth to confirm detection of calcium and expected demineralization maps on carious teeth.

A Clinical Evaluation was performed, taking in to account the “mock-mouth” bench-top studies, pre-clinical studies on extracted teeth and clinical studies of similar comparator devices. In addition, pre-clinical toxicology studies on the Disclosing Solution (cytotoxicity, oral toxicity, oral irritation and sensitisation tests) were also carried out according to ISO10993 and American Dental Association guidelines. The Clinical Evaluation Report concluded that sufficient clinical data was available to support the safety and performance of the Calcivis System, without the need for a specific clinical study.

The Calcivis System was CE marked in December 2013, following submission of the Technical File.

In May 2014, the first formal Post-Approval Clinical Study was performed in adults (16 to 25 yrs old) using the advanced prototype Calcivis System. The Primary Objectives of the study were to assess the Performance and Safety of the Calcivis System, and the Secondary Objective was to assess user experience with the Calcivis System (both User and Patient). A total of 42 patients were recruited to the study from three UK, General Dental Practices, to obtain a total of 31 evaluable patients. Eligible patients were those with interpretable images of both a tooth with no visible lesion identified (ICDAS Code 0) and a tooth with a suspected visible lesion identified (ICDAS Code 1, 2 or 3). Images from 11 patients were not eligible for interpretation due to confounding factors including ambient light ingress, gross saliva contamination and poor disclosing solution coverage on the tooth surface. All these issues have been addressed in the design phase for the new commercial Calcivis System which is the subject of this study.

All 42 patients were included in the Safety Population – two adverse events were recorded – bleeding gums and slight gum abrasion – both were device-related, non-serious and asymptomatic to the patients with no action required. One other adverse event was recorded as a device deficiency when the device jammed and did not dispense fluid.

31 patients were included in the Agreement Population – analysis of the level of agreement between the ICDAS scores and elevated luminescence, (Y/N) as defined by the Investigators.

For the primary study objectives, the study results concluded that: -

1. The Calcivis System was safe in clinical use as determined by the low number and minor nature of the adverse events recorded.
2. Analysis of the overall level of agreement between elevated luminescence and the presence of lesions predicated as active by the Investigators showed agreement in 47 of the 65 teeth imaged (72.3 %) which was statistically significant, not due to chance and above the expected level of 70%.

(Of the 31 teeth identified by the Investigators with no visible lesions, 26 showed no elevated luminescence using the Calcivis System – corresponding to a negative percentage agreement of 83.9%. Of the 34 teeth with visible lesions identified by the Investigators, 21 showed elevated luminescence using the Calcivis System – corresponding to a positive percentage agreement of 61.8%).

A recent paper by Alves et al (¹¹) indicates an association between the stage of eruption and activity status of caries. As summarized in table below:

Stage of Eruption	1	2	3	4
sound	526	108	814	694
inactive non-cavitated	9	5	148	164
active non- cavitated	184	43	179	48
Total caries non- cavitated	193	48	327	212
% act non- cavitated	95	90	55	23

stage 1, partially erupted occlusal surface;

stage 2, fully erupted occlusal surface, <1/2 crown exposed; and

stage 3, fully erupted occlusal surface, >1/2 crown exposed

stage 4. Full occlusion

The teeth examined in the clinical study were predominantly stage 3 i.e. *fully erupted occlusal surface, with greater than half the crown exposed* with expected activity in approx. 55% of lesions.

For the secondary study objective, the study results concluded that: -

Although one patient recorded ‘marked pain’ on the Patient Questionnaire, the overall feedback was positive with 91.4% of patients recording their experience with the Calcivis System as ‘good’ or ‘very good’. 88.1% of patients reported that seeing the images of their teeth and having the dentist explain their situation was ‘helpful’ or ‘very helpful’. 65% of the dentists recorded their overall user experience with the Calcivis® System to be ‘good’.

5.8 Device Accountability

All study devices will be accounted for. Master Device Accountability records will be maintained by the Sponsor for all device components – intra-oral imaging device kit, disclosing solution kits and application kits.

Each Investigator will be provided with one intra-oral imaging device for use in the study, and a sufficient number of disclosing solution kits and application kits, for the target number of patients to be recruited. Additional supplies of all three components will be available, should they be required.

Each site will maintain Device Delivery and Return documentation. All intra-oral imaging devices, and unused disclosing solution kits and application kits will be returned to Calcivis Ltd at the end of the study period.

Returned study devices / components will be checked against the Master Device Accountability records by the Sponsor. Any discrepancies will be documented and investigated.

5.9 Device Labelling and Storage

The Intra-Oral Imaging Device Kit will be supplied as a single unit, non-sterile and will be identified by a unique serial number.

The single-use Disclosing Solution Kits will be supplied in non-sterile boxes, each box containing 10 vials each of the freeze-dried protein and water for reconstitution. In addition each box will contain a snapper for safe opening of the vials. Each vial will be identified by a unique lot number.

The Application Kits will be supplied in boxes of ten, each kit containing an individually wrapped applicator, an individually wrapped, sterile, off- the- shelf syringe, and an individually wrapped, sterile, off- the- shelf needless adaptor. The individual Applicators will be identified by a unique lot number.

The Calcivis multi-use format will be supplied in a non-sterile box, containing 1 x 5ml vial of freeze-dried photoprotein and individually wrapped adaptor, 1 x 5ml vial of diluent and individually wrapped adaptor, 10 x individually wrapped sterile, off-the-shelf single-use syringes and 10 x individually wrapped single-use applicators.

The Intra-Oral Imaging Device and Application Kits will be stored at room temperature, and will be held in a secure area at site when not in use. The Disclosing Solution Kits, containing the lyophilised protein and Calcivis diluent for reconstitution, will be stored in a secure area not above 25⁰ C. For the Calcivis multi-use format, once reconstituted the vial of Photoprotein will be stored at 2 to 8⁰ C, up to a maximum of 4 weeks.

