Inclusion and Exclusion Criteria	
Inclusion criteria
 
 1. Patient must be \geq 12 years old 2. Patient must have had orthodontic appliances placed on the upper incisors and / or canines for at least 12 months, and be ready for de-bond 3. Patient must have at least one, active white spot lesion identified by the Calcivis System immediately post de-bond 4. Patient and / or parent or guardian must be willing and able to give written informed consent 5. Patient and / or parent or guardian must be willing and able to adhere to study schedule 
Exclusion criteria
 
 1. Any Patient with recent tooth bleaching (within previous two weeks of imaging with the Calcivis System) or within the follow-up period 2. Any patient currently taking part in a clinical research study, or who has taken part in a clinical research study in the previous three months 3. Pregnant and / or nursing mothers
Control	There will be no Control teeth for this study
Number of Patients	Up to 100 patients may have to be recruited, to obtain 45 eligible patients for follow-up

Statistical Rationale	
The sample size of 45 patients (with potentially a maximum of five teeth per patient) is not based on statistical power considerations, but as a number of patients that will enable useful data to be collected on the functionality and safety of the Calcivis System for assessing the activity of post-Orthodontic lesions. In addition the data may be used to support the design of future clinical studies.
 
The percentage of teeth showing luminescence using the Calcivis System will be summarised for each post-baseline visit. Additionally the percentage of teeth showing luminescence will be summarised for each post-baseline visit by Investigator and ICDAS score at Visit 1.
 
For each subject the percentage of teeth with each ICDAS score will be calculated. This will then be summarised over all subjects for each post-baseline visit. The ICDAS score will also be cross-tabulated with the presence/absence of luminescence from individual teeth for each visit.
 
User and patient questionnaire data will be summarised descriptively for each visit.
 
Adverse events during the course of the study will also be summarised descriptively.
 
All patients on which the Calcivis System was used at least once will be included in all analyses.

Number of Sites	One (1)

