4. STUDY OBJECTIVES AND ENDPOINTS

4.1 Primary Objective

Primary Objective - to assess the Calcivis System for monitoring the activity levels of post-orthodontic treatment white spot lesions as an indicator of either 1) gradual arrest of lesion activity (remineralisation / repair) or 2) continuing lesion activity (on-going demineralisation) of the Calcivis System –

this will be measured by bioluminescent output over time from baseline (de-bond) to 8 weeks post be-bond (presence or absence of bioluminescence)

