7.2 Patient Selection and Confidentiality

Patients will be recruited to the study from an NHS hospital, orthodontic clinic. Patients will initially be identified and selected according to Inclusion Criteria and the Exclusion Criteria listed below from those attending for orthodontic treatment and who are ready for de-bond. Patients must provide written informed consent (or parents or guardians where the patient is not competent to provide written informed Consent), and be willing to adhere to the study schedule, before being entered in to the study, however, only patients who have 'active' lesions on de-bond, as confirmed with the Calcivis System at the baseline visit, will be followed up in this study. If all lesions are assessed as 'inactive', the patient will be withdrawn from the study.

It is expected that up to 100 patients may have to be recruited and imaged with the Calcivis System at de-bond (baseline), in order to find 45 patients with active lesions.

Patients will be encouraged to complete all Study Visits, however, patients are free to withdraw Consent at any time, irrespective of their initial consent. Patients may also be withdrawn from the study by the Investigator on the grounds of safety. Any patients who withdraw or are withdrawn from the study will be replaced.

All patients recruited to the study will be identified by a unique study number, comprising the site number and a patient number, to allow any data collected on them to be anonymised. The investigator will maintain a confidential patient identification list of all patients enrolled in the study (by name and patient number). The list will be maintained at the site and will not be retrieved by the Sponsor.

Only patients with 'active' lesions will be followed up in this study, therefore no randomization will be required.

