7.3 Study Duration

The overall study period is expected to take 18 months - 3 months for Ethics Committee and NHS, R & D approvals, 12 months for recruitment and study procedures, and 3 months for final follow up, data collection and analysis.

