8.2 Study Visit 1 – de-bond - baseline

At this visit, written Informed Consent (ref. 15.3) will be taken by the Investigator and the following information collected and procedures carried out.

Pre-Imaging Information collected

Demographics – DoB and gender

Relevant medications – calcium supplements and antacids

Oral hygiene information – routine brushing regime, toothpaste and any other dental products used

Orthodontic history – date braces applied, type of bracket, ligation used, and any other relevant information (e.g. re-mineralization products used)

Preparation of the Calcivis System

The Calcivis System must be prepared according to the manufacturer's Instructions For Use. Single-use Disclosing Solution (Photoprotein) should not be reconstituted more than 2 hours before the first tooth is imaged. Once reconstituted, the multi-use vial of Disclosing Solution (Photoprotein) should be stored at 2 to 8^o, up to a maximum of 2 weeks.

Teeth Preparation Procedure

Immediately after the appliances have been removed, up to a maximum of four teeth from any of the four upper incisors and two canines with visible white spot lesions on de-bond, will be identified and recorded for assessment using the Calcivis System.

Each free smooth surface will be air dried before taking close-up colour photographs of the tooth or teeth with a digital camera for reference, and coded for ICDAS (1,2 or 3).

All relevant teeth will then be cleaned by the Orthodontist, by brushing with water, and rinsing with water and an air-water spray from a conventional dental 3-in-1 device, according to the Tooth Cleaning Protocol (Appendix 2). Patients will be asked to rinse out thoroughly with tap water.

Imaging with the Calcivis device

Extreme care must be taken to ensure the surface of the tooth and surrounding area are free from saliva before imaging with the Calcivis System by air drying for a minimum of 10 seconds immediately before application of the disclosing solution and Calcivis System imaging.

Images of the free smooth tooth surfaces, will be taken with the Calcivis System according the Instructions For Use. If the first image of a selected tooth is not clear, it is acceptable to take a second image of the selected tooth, however patients must rinse out with water before the subsequent image

can be taken, and the tooth air-dried as described above. A maximum of four images per patient can be taken with the Calcivis System.

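### Section 5.9 allows the reconstituted multi-use photoprotein vial 4 weeks in storage, while 8.2, 8.3 and 8.4 limit the same vial to 2 weeks

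*Protocol*

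**What the plan says.** Section 5.9 is the protocol's section on labelling and storage. It says that the multi-use vial, once reconstituted, is kept refrigerated at 2 to 8 °C "up to a maximum of 4 weeks".

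Sections 8.2, 8.3 and 8.4 each contain a paragraph on preparing the system. Each says that the reconstituted multi-use vial is kept at 2 to 8 degrees "up to a maximum of 2 weeks".

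The reagent in that vial produces the primary reading. Section 4.1 measures the primary objective by "presence or absence of bioluminescence" from de-bond to 8 weeks, and at each visit the investigator records activity as yes or no from the images. The Synopsis adds: "There will be no Control teeth for this study".

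The single-use kit is an alternative. The Synopsis and section 5.2 list the two formats as and/or, so the storage limit matters only where the multi-use format is used.

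**The concern.** A handling rule for the reagent that generates the primary measure should have one value throughout the plan. Here it has two, differing by a factor of two, and nothing in the protocol says which prevails. Section 5.9 is where a reader would look for storage rules. It is also worded more firmly (will, against should in the visit sections), and it gives the looser limit.

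Two things are at stake:

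- **Whether the vial may be used.** For a vial on day 20, the storage section says yes and the visit sections say no.
- **Whether its use is a deviation.** Section 14.3 requires every deviation to be documented, reported to the sponsor and assessed for its impact on patient safety. For the same vial, the plan does not settle whether there is anything to report.

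Section 6.1 names deterioration of the disclosing solution over its shelf life, and contamination of the re-used vial, among its high-impact risks. A storage limit is the kind of rule that bears on both. With no control teeth, the study has no built-in comparison that would show a weak batch of reagent.

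**Working it through.** No sample size, power or error-rate figure is involved. The check sets the four statements side by side and then measures the overlap.

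| Section | Item | State | Temperature | Limit |
|---|---|---|---|---|
| 5.9 | multi-use photoprotein vial | reconstituted | 2 to 8 °C | 4 weeks |
| 8.2 (Visit 1) | multi-use photoprotein vial | reconstituted | 2 to 8 degrees | 2 weeks |
| 8.3 (Visit 2) | multi-use photoprotein vial | reconstituted | 2 to 8 °C | 2 weeks |
| 8.4 (Visit 3) | multi-use photoprotein vial | reconstituted | 2 to 8 °C | 2 weeks |

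**Can the limits be reconciled?** The product, its state and the temperature agree in all four places, so the limits cannot belong to different formats or conditions.

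**Is this only a difference from the revision history?** No. All four statements are current Version 5 text. The history helps only with intent: its Version 4 entry records a cut from 4 weeks to 2 weeks and lists it for the study-visit pages. That suggests 2 weeks is the intended value and that 5.9 was not brought into line.

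**Size of the overlap.**
- Limit in 5.9: 4 × 7 = 28 days.
- Limit in 8.2 to 8.4: 2 × 7 = 14 days.
- Ages allowed by 5.9 and barred by the visit sections: days 15 to 28, which is 28 − 14 = 14 days.
- Share of the life that 5.9 permits: 14 / 28 = 50%.

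**Does the overlap meet the visit schedule?** The Schedule of Events puts Visit 2 at 25 to 31 days after de-bond. A vial reconstituted on the day of a patient's Visit 1 would be 25 to 28 days old in the first part of that window. Section 5.9 would allow it and 8.3 would not. This shows that the conflict could arise on the plan's own schedule. It does not show that it did.

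**Effect on the results.** The documents give no figure for loss of light with vial age, so no tooth count or percentage can be derived.

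**The case against.** The strongest reply is that this is an editorial leftover with little room for misuse. The sections that instruct the operator at the chair all say 2 weeks. A vial of 14 days or less satisfies every section, so anyone who follows the whole plan has a safe reading. Preparation must also follow the manufacturer's Instructions For Use, which are not shown. Staff are trained in preparing the solution (5.10), and sponsor representatives are available at the visits (8.2). All of that stands and keeps the point minor. It lowers the practical risk but does not correct 5.9.

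The protocol also gives no reason for the 2-week limit. It could be microbiological as easily as a matter of light output. Section 6.1 rates the listed risks as very low in likelihood and adequately addressed, with stability studies cited for deterioration. That stands too.

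A reader might infer more than the text supports in three ways:

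- **That over-age reagent inflates apparent lesion arrest.** The documents do not show that light output falls between days 15 and 28. Even if it did, the net direction would be open. Weak reagent at baseline would remove teeth from follow-up, because 8.2 follows only teeth that show luminescence, while weak reagent at follow-up would add to apparent arrest.
- **That vials were in fact used past day 14, or that every visit is affected.** The documents do not give the rate of use, the number of vials open at once or the share of visits using the multi-use format.
- **That the single-use format has a matching contradiction.** Its 2-hour limit runs from reconstitution in 8.2 and from drawing into the syringe in 8.3 and 8.4. This is uneven wording. Section 5.5 calls for reconstitution immediately before use, and the unseen instructions may say more. It is no part of this point.

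**Conclusion.** The inconsistency is real, minor and certain on the face of the text. Section 5.9 is wrong as written when set against 8.2, 8.3 and 8.4. For the multi-use format the plan gives opposite answers over vial ages of 15 to 28 days: whether the reagent may be used, and whether using it is a deviation.

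The 14-day overlap is the only size the documents support. It rests on reading weeks as 7 days and on nothing else. No bias in the luminescence percentages and no safety effect is shown, and either may be nil. That 2 weeks is the right value rests on three current sections agreeing, on its being the stricter limit, and on the direction of change in the revision history.

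**What to change.** In section 5.9, change the storage limit for the reconstituted multi-use vial so that it reads "up to a maximum of 2 weeks". Sections 8.2, 8.3 and 8.4 stay as they are.

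The cost is one number in one sentence, which can go into the next written amendment under section 14.2. The case report form, sample size, visit schedule and analysis are unaffected. Until the text is corrected, a note to the site that the 2-week limit governs would remove the ambiguity, and a vial kept to that limit complies with every section.
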